5.1.10.5 Ocular

In the event of suspected clinically significant findings (e.g., macular edema), an unscheduled ophthalmology and OCT examination should be performed. The OSB will receive all information related to suspected cases of macular edema and will perform central review of OCT results and subject data. In the case of macular edema confirmed by the local ophthalmologist, the subject must be discontinued from study drug and will be managed and followed-up until resolution or until medically indicated. Any clinically relevant finding found after study drug initiation and during the follow-up period and meeting the definition of an AE will be recorded accordingly in the eCRF.

5.1.10.6 Reproductive/pregnancy

If a subject becomes pregnant while on ponesimod, ponesimod must be discontinued. Female subjects participating in the study and wishing to become pregnant during the study must discontinue ponesimod.

5.1.10.7 Respiratory

Subjects experiencing new or worsening persistent respiratory symptoms must be carefully evaluated. Lung infections are common in chronic GVHD, and should be suspected, especially in case of fever and cough. BOS is an uncommon and serious condition in chronic GVHD and is associated with irreversible pulmonary function decline which does not respond to bronchodilators. Ponesimod can cause pulmonary function decline which is reversible upon cessation of drug and which is also reversible with bronchodilators.

Lung function testing, including spirometry, is assessed frequently in this study. **Investigators may conduct unscheduled spirometry at any time, and should do so particularly in case of unexplained respiratory symptoms.** Spirometry results may

Confidential

require a subsequent bronchodilator challenge, the results of which may lead to premature ponesimod discontinuation and further diagnostic work up to exclude/diagnose BOS or other lung disease.

Bronchodilator challenge is required if all of the following spirometry parameters are met at any time:

- > 10% decrease from the study baseline FEV₁, and
- FEV₁ < 60% predicted, and
- FEV₁/FVC < 0.7

Further dose escalation is prohibited once these parameters have been met.

Bronchodilator challenge

Subjects undergo bronchodilator challenge to help distinguish pulmonary function decline due to ponesimod from potential BOS or other causes.

Procedure for bronchodilator challenge

- An initial PFT assessment is performed.
- Then, four separate inhalations (puffs) of 100 µg salbutamol/albuterol are administered using a spacer device.
- A second PFT assessment must be performed 30 minutes (\pm 15 minutes) after administration of salbutamol/albuterol.

Ponesimod may be continued, without interruption, if all of the following parameters are met following bronchodilator challenge:

- FEV₁ \geq 60% predicted, and
- FEV₁/FVC \geq 0.7, and
- FEV₁ \leq 10% decrease from study baseline and
- Subjects on 5 mg are not experiencing respiratory symptoms (this parameter does not apply to subjects on 10 or 20 mg).

For continuing subjects, refer to the box: “CONTINUATION (after successful bronchodilator challenge)”.

If these parameters are not met, ponesimod must be prematurely discontinued and further assessment is required; refer to the box: “PREMATURE DISCONTINUATION (after failing bronchodilator challenge)”.

Confidential

CONTINUATION (after successful bronchodilator challenge)

Generally, subjects are continued on ponesimod at the current dose, and no further dose escalation is allowed. If following a successful bronchodilator challenge, the conditions for performing the bronchodilator challenge are met again, a new bronchodilator challenge is recommended but not required and may be performed at the discretion of the investigator.

For those subjects on ponesimod 10 mg or 20 mg, immediate dose reduction to 5 mg or 10 mg may be considered by the investigator if subjects have respiratory symptoms. Dose escalation is not allowed after dose reduction in this study.

For subjects continuing ponesimod, spirometry testing is conducted at all subsequent scheduled visits. In case of a recurrent 10% decline versus study baseline in FEV₁, or continuing or worsening respiratory symptoms following dose reduction, subjects must be prematurely discontinued.

PREMATURE DISCONTINUATION (after failing bronchodilator challenge)

If the subject fails the bronchodilator challenge, ponesimod as the cause of lung function decline is still not ruled out. Ponesimod effects on lung function reverse rapidly within a few days following cessation of drug intake. Therefore, a rapid and robust improvement in lung function is required to help confirm ponesimod induced lung function decline and simultaneously help exclude BOS (which is not reversible).

Spirometry must be conducted 7 to 10 days following premature discontinuation.

Pulmonary function decline is very likely due to ponesimod, and BOS is unlikely if:

- FEV₁ assessed 7 to 10 days post premature discontinuation returns to baseline FEV₁.

All prematurely discontinued subjects need follow-up monitoring and evaluation. See box: “MONITORING AND WORK-UP for prematurely discontinued subjects”.

MONITORING AND WORK-UP for prematurely discontinued subjects

In all cases of premature discontinuation, monitoring must be provided until respiratory AEs have resolved and changes in pulmonary function are no longer regarded as clinically relevant, or until medically indicated.

Further diagnostic work-up and consultation with a pulmonologist or other specialist is required and should be in accordance with local practice if PFT abnormalities or respiratory symptoms persist.

Confidential

The current recommended work-up for BOS includes PFT testing and expiratory computed tomography (CT). Because a new diagnostic technique for BOS termed parametric response mapping is currently under investigation, a high resolution (helical) CT of inspiration and expiration is encouraged if available. This technique will permit visual representation of lung affected by obstructive disease (BOS) versus lung tissue with normal aeration or restrictive disease, and may become a valuable measure in the future [Jagasia 2015].

Use of short-acting β_2 agonist for subjects continuing on ponesimod

Subjects experiencing respiratory symptoms or reduced pulmonary function during the course of the treatment with ponesimod and fulfilling criteria to continue study medication may be prescribed short-acting β_2 agonist (to be used on an 'as needed' basis / 'PRN' use), at the investigator's discretion.

For all subjects: any clinically relevant finding found after signing of informed consent and during the follow-up period and meeting the definition of an adverse event will be recorded accordingly in the eCRF.

5.2 Mandatory concomitant chronic GVHD treatment (Core Treatment Period only)

Section 5.2 applies only to the Core Treatment Period.

5.2.1 Immunosuppressant treatments other than ponesimod

Along with the study drug ponesimod, subjects must be treated with systemic glucocorticoids AND/OR one of the following systemic agents: CsA, TAC, MMF, MPS, EVL, SRL, or MTX.

5.2.2 Modifications to IS treatments

Mandatory and allowed (e.g., topical IS) IS therapies make up the subject's background chronic GVHD IS therapy during the study. The dose and frequency of these medications should be kept constant during the study.

Systemic glucocorticoids

Glucocorticoid dosing should not be increased or decreased during the course of the study, with the following exceptions:

- The investigator may see reason to initiate or increase the dose of systemic glucocorticoid to treat chronic GVHD flare or another condition. In this case, the investigator should consult with the sponsor prior to initiation or dose increase and the

Confidential

reason for dose increase should be documented. The subject may continue on ponesimod. The prednisone equivalent dose should never exceed 1 mg/kg/day.

- Systemic glucocorticoid dosing may be lowered to avoid or prevent short- and long-term glucocorticoid toxicity. For subjects on longer term glucocorticoid therapy, it is recommended that the dose reduction rate does not exceed 10% of dose per week. Glucocorticoid dosing may be increased following reduction, if medically indicated.
- Systemic glucocorticoid dosing is not subject to restrictions during the Extension Treatment Period.

Mandatory systemic IS other than ponesimod or systemic glucocorticoids

Systemic IS dosing (mg daily dose) should not be increased above baseline dose during the course of the study, with the following exception:

- Systemic IS blood or serum level is below the therapeutic range that was defined for the subject at the time of entry into the study. The dose should be increased to restore blood or serum levels to within the defined therapeutic range. (ISs that are not monitored with blood or serum level monitoring may never be increased above baseline dose.)

Systemic IS dosing (mg daily dose) should not be lowered during the course of the study, with the following exceptions:

- AE or intolerance due to the systemic IS. The dose should be sufficiently lowered or discontinued, per investigator judgment.
- Systemic IS blood or serum level is above the therapeutic range that was defined for the subject at the time of entry into the study. The dose should be lowered to restore blood or serum levels to within the defined therapeutic range.

Topical CNIs or glucocorticoids

- The sponsor recommends not starting or increasing dosage of topical CNI or topical glucocorticoid therapy during the course of the core study.
- Topical CNIs or glucocorticoid therapy dosing or area of application should not be decreased during the course of the core study, unless there is an AE or intolerance due to the topical drug. The dose should then be sufficiently lowered or discontinued, per investigator judgment.

5.3 Previous and concomitant therapy

Section 5.3 applies to both Core and Extension Treatment Periods.

5.3.1 Definitions

A previous therapy is any treatment for which the end date is prior to the start of study (i.e., signing of initial informed consent).

Confidential

All therapy that is study-concomitant (i.e., ongoing or initiated after signing of informed consent, and initiated before EOS visit) must be captured in the eCRF.

5.3.2 Reporting of previous HSCT and GVHD therapies

Previous HSCT and GVHD therapies will be collected as part of HSCT and GVHD history [see Section 4.5].

5.3.3 Reporting of concomitant therapy in the eCRF

The use of all study-concomitant therapy (including contraceptives and traditional or alternative medicines, i.e., plant-, animal-, or mineral-based medicines) will be recorded in the eCRF. The generic name, start/end dates of administration (as well as whether it was ongoing at start of treatment and/or EOS), route, dose, frequency, and indication will be recorded in the eCRF.

5.3.4 Allowed concomitant therapy

- Administration of i.v. atropine in the event of symptomatic bradycardia
- Topical glucocorticoid
- Topical CNI
- Oral budesonide
- QT-prolonging drugs with known risk of Torsades de Pointes should be used with caution since ponesimod may potentially enhance their effect on QT interval (list of drugs and guidance are provided in Appendix 3)
- Short-acting β 2 agonists for respiratory symptoms and/or reduced pulmonary function during ponesimod treatment
- Vaccination with non-live vaccines (*Note:* although nonclinical data indicate no significant impairment of antibody response to immunization, no clinical data is currently available on vaccination efficacy under ponesimod treatment, therefore it is suggested that all planned/indicated vaccinations are completed more than 30 days before the start of treatment and, in case of vaccination during the study, titer control is recommended.)
- Other treatments considered necessary for the subject's benefit and not categorized as prohibited concomitant medications

5.3.5 Forbidden concomitant therapy

- IS or immunomodulatory treatments other than those prescribed per protocol
- Retinoids
- Thoracoabdominal irradiation
- Mesenchymal stem cell therapy

- Extracorporeal photopheresis
- Vaccination with live vaccines
- β -blockers, diltiazem, verapamil, digoxin, digitoxin or any other anti-arrhythmic or HR-lowering systemic therapy (a non-exhaustive list of drugs provided in Appendix 4)
- Any other investigational drug

6 STUDY ENDPOINTS

This section describes the Core Treatment Period endpoints only. Similar endpoints will be assessed for the Extension Treatment Period, however adjusted for the corresponding visit schedule.

6.1 Pharmacokinetic and pharmacodynamic endpoints

6.1.1 Pharmacokinetic evaluations

- Trough concentrations (C_{trough}) concentrations of ponesimod at Day 1, and Weeks 4, 8, 12, 16, and 20 (all samples pre-dose), and Week 24
- Ponesimod concentration 3 hours post-dose at Day 1 and Week 12

6.1.2 Pharmacodynamic evaluations

Primary PD endpoint

- Change in peripheral absolute lymphocyte count from baseline to Week 4, Week 8 and Week 12

The primary endpoint assesses intra-subject dose response during the first 12 weeks of treatment.

Other PD endpoints

- Peripheral absolute blood lymphocyte count change from baseline (pre-dose on Day 1) to Weeks 4, 8, 12, 16, 20, 24, and FU1, and change from pre-dose Week 12 to 3 hours post-dose Week 12.
- Peripheral absolute lymphocyte count reversibility from EOT1 to FU1 expressed as absolute change and percent change from baseline

6.1.3 PK/PD relationship

The PK and selected efficacy and safety variables will be correlated with the PD (peripheral absolute lymphocyte count and magnitude of reduction of lymphocyte count). If deemed appropriate, the PK will also be correlated with selected safety variables.

Confidential

6.2 Safety endpoints

The treatment-emergent period is defined as the time from first study drug intake up to 30 days (inclusive) after last study drug intake.

6.2.1 Overall safety endpoints

- Treatment-emergent AEs, serious adverse events (SAEs), and AEs of special interest [see Appendix 5]
- AEs leading to premature discontinuation of study drug
- Deaths

6.2.2 Absolute lymphocyte count

- Treatment-emergent absolute lymphocyte count $< 0.2 \times 10^9/\text{L} (< 200 \text{ cells/mm}^3)$

6.2.3 Cardiac rate and rhythm safety endpoints

- Treatment-emergent morphological ECG abnormalities (as defined by the ECG provider)
- Change in 12-lead ECG variables (HR, PR, QRS, QT, QT corrected for HR on the basis of Bazett's formula [QTcB], QT corrected for HR on the basis of Fridericia's formula [QTcF]) from pre-dose to selected post-dose assessments (1 h, 2 h, 3 h, 4 h) on Day 1 and on day of re-initiation of study drug.
- Notable abnormalities for selected 12-lead ECG variables (HR, PR, QT, QTc) at 3 hours post-dose assessment on Day 1, pre-dose on Weeks 4, 8, and 12, and Week 24 (notable abnormalities definition in Appendix 6).
- Cardiac safety events will include:
 - Treatment-emergent QTc $> 450 \text{ ms (male), } > 470 \text{ ms (female), } > 500 \text{ ms (male), and } > 520 \text{ ms (female)}$
 - Treatment-emergent QTc increase from baseline $> 30 \text{ ms, } > 60 \text{ ms}$
 - Other treatment-emergent abnormalities observed by 12-lead ECG
 - Treatment-emergent (serious) cardiac AEs of special interest.

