1.3.2.4 Safety and tolerability

Clinical studies to date have identified transient changes in heart rate (HR) and atrioventricular (AV) conduction as the most prominent safety-related signal with ponesimod. Oral doses of ponesimod resulted in dose-dependent sinus rate reductions in all treated subjects; the changes were transient, with a nadir at approximately 1.5–2.5 hours post-dose, and resolved largely within 6–10 hours after dosing. In some subjects, these HR reductions were accompanied by a transient effect on AV conduction with prolongation of the PR interval on the electrocardiogram (ECG) and, occasionally, second degree AV-block. The effects on HR and AV conduction diminish with repeated administration of ponesimod, indicating desensitization. To minimize the first-dose effects on HR and AV conduction, a dose up-titration regimen was successfully tested and is implemented in current clinical trials.

Difficulty in inspiration (dyspnea) and related pulmonary function test (PFT) changes have also been detected in humans. Mild transient dyspnea/cough was noted frequently 2–6 h after an oral dose of 40 mg or higher. Symptoms resolved spontaneously upon discontinuation of treatment with ponesimod. Dose-dependent decreases from baseline in forced expiratory volume in 1 second (FEV₁) were observed in the ponesimod groups. These decreases were established within the first few weeks, remained stable thereafter (including over long-term treatment), and were fully reversible following treatment discontinuation.

Confidential

Elevations of aspartate transaminase (AST) and/or alanine aminotransferase (ALT) without any bilirubin increase have been noted with ponesimod; they have been reversible upon discontinuation of dosing. The changes were asymptomatic.

Individual cases of macular edema associated with changes in visual acuity have been observed in subjects treated with ponesimod. These events resolved upon discontinuation of ponesimod.

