5.1.7 Cardiac monitoring for ponesimod initiation and re-initiation requiring re-up titration

Subjects must undergo cardiac monitoring at the site on Day 1 (Visit 2 - ponesimod initiation) and EX-1 (Visit 11 - ponesimod treatment initiation in the extension).

Subjects must also undergo cardiac monitoring at the site on the first day of any ponesimod re-initiation requiring up-titration.

Cardiac monitoring is overseen by the cardiac safety assessor and consists of the following:

- Pre-dose: 12-lead ECG; systolic/diastolic BP measurement.
- Hourly post-dose, starting 1 hour post-dose: 12-lead ECG; systolic/diastolic BP measurement. ECG and BP are recorded hourly until the subject is discharged from monitoring.
- Discharge from monitoring at least 4 hours post-dose, as per “Discharge from Cardiac Monitoring Criteria” below.

Discharge from Cardiac Monitoring Criteria

After the collection of the 12-lead ECG and systolic/diastolic BP measurement at 4 hours post-dose and up to 12 hours post-dose, the subject may be discharged from the clinic and continue on ponesimod as soon as all of the following are met:

- ECG-derived resting HR > 45 bpm on the last ECG. If ECG-derived resting HR < 50 bpm on the last ECG, then HR at last ECG must be higher than at least one HR recorded on any prior post-dose ECG.
- SBP > 90 mmHg.
- QTcF < 481 ms on the last ECG.
- Increase in QTcF on the last ECG versus pre-dose ECG must be < 60 ms.
- No persisting significant ECG abnormality (e.g., QT prolongation, AV block second degree or higher) or ongoing AE requiring continued hospitalization or prohibiting study continuation as an outpatient.

Should the subject not meet the criteria for discharge at 12 hours post-dose, he/she must be discontinued from ponesimod. Subjects who are discontinued may be discharged from the monitored setting only after the following criteria are met:

- Vital signs return to near baseline values.
- No persisting ECG abnormality (e.g., AV block second degree or higher).
- No ongoing AE requiring continued hospitalization.
- Absence of any other medical indication to remain in the monitoring setting.

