11 STATISTICAL METHODS

All statistical analyses will be conducted by Actelion or by designated contract research organizations supervised by Actelion.

The Statistical Analysis Plan (SAP) will be approved prior to database lock for the final analyses. The SAP provides the full details of all analyses, data displays, and algorithms to be used for data derivations.

All data will be listed, and endpoints will be summarized by appropriate descriptive statistics (tables or figures), typically including:

- Number of non-missing observations, number of missing observations, mean, standard deviation (STD), median, Q1, Q3, minimum and maximum for continuous endpoints;
- Number of non-missing observations, number of missing observations and frequency with percentage per category (percentages based on the number of non-missing observations) for categorical endpoints;
- Number of subjects at risk, cumulative number of events, cumulative number of censored observations and Kaplan-Meier estimates of the survival function for time-to-event endpoints.

Absolute changes from baseline are defined as: post-baseline value minus baseline value, i.e., a positive sign indicates an increase as compared to baseline.

A percentage (relative) change from baseline is defined as the absolute change from baseline divided by the baseline value (if the baseline value not equal 0) multiplied by 100.

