11.2.10.3 Cardiac Safety

11.2.10.3.1 Treatment-emergent morphological ECG abnormalities (as defined by the ECG provider)

Treatment-emergent morphological ECG abnormalities will be summarized descriptively for the Core Treatment Period and for the Extension Treatment Period.

11.2.10.3.2 12-lead ECG assessments

Descriptive summary statistics, by time and visit, will be provided for observed treatment-emergent values and absolute changes from baseline in numeric 12-lead ECG values (HR, PR, QRS, QT, QTcB and QTcF). Data will be summarized from pre-dose to the post-dose assessments at 1 h, 2 h, 3 h and 4 h on Day 1. 12-lead ECG data will also be summarized for the Extension Treatment Period.

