11.2.10.3.3 Notable abnormalities for selected 12-lead ECG variables

Notable abnormalities for selected 12-lead ECG variables (HR, PR, QT, QTcF) will be summarized for all data at the 3-hour post dose assessments on Day 1 and pre-dose at Weeks 4, 8, 12, and 24. Notable abnormalities will also be summarized for the Extension Treatment Period.

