11.2.10.3.4 Cardiac safety events

Cardiac safety events will include:

Confidential

- Treatment-emergent QTc > 450 ms (male), > 470 ms (female), > 500 ms (male), and > 520 ms (female)
- Treatment-emergent QTc increase from baseline > 30 ms, > 60 ms
- Other treatment-emergent abnormalities observed by 12-lead ECG
- Treatment-emergent (serious) cardiac AEs of special interest.

Cardiac safety events will be summarized descriptively for the Core Treatment Period and for the Extension Treatment Period.

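### Day 1 HR and PR outliers are counted only on the 3 h ECG, after the stated heart-rate nadir, so the proportions can only equal or understate those over all post-dose ECGs

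*Combined protocol and SAP*

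**What the plan says.** Section 6.2.3 lists as a cardiac endpoint "Notable abnormalities for selected 12-lead ECG variables (HR, PR, QT, QTc) at 3 hours post-dose assessment on Day 1", followed by pre-dose ECGs at Weeks 4, 8 and 12 and the Week 24 ECG. The synopsis and Section 11.2.2 repeat this. Section 11.2.10.3.3 says that these abnormalities "will be summarized for all data at the 3-hour post dose assessments on Day 1 and pre-dose at Weeks 4, 8, 12, and 24", and that they will also be summarised for the extension.

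On the time course of the first-dose fall in sinus rate, Section 1.3.2.4 says "the changes were transient, with a nadir at approximately 1.5–2.5 hours post-dose, and resolved largely within 6–10 hours after dosing". On conduction it says "In some subjects, these HR reductions were accompanied by a transient effect on AV conduction with prolongation of the PR interval", without a separate time of peak.

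On data collection, Section 5.1.7 requires, after the pre-dose ECG, "Hourly post-dose, starting 1 hour post-dose: 12-lead ECG; systolic/diastolic BP measurement", until discharge from monitoring at 4 to 12 h. This applies on Day 1, at EX-1 and on the first day of any re-initiation with up-titration. Section 7.3.1 has the ECGs recorded digitally and read centrally.

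Three other planned outputs bear on the same tracings:
- Section 11.2.10.3.2 covers continuous ECG values: "Data will be summarized from pre-dose to the post-dose assessments at 1 h, 2 h, 3 h and 4 h on Day 1". The default statistics in Section 11 are "mean, standard deviation (STD), median, Q1, Q3, minimum and maximum for continuous endpoints", and all data are to be listed.
- Section 11.2.10.3.4 counts QTc above 450, 470, 500 and 520 ms (by sex) and QTc increases above 30 and 60 ms as treatment-emergent events. Section 6.2 starts that period at first intake.
- Morphological findings, other ECG abnormalities and cardiac adverse events of special interest are summarised with no fixed hour.

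Appendix 6 leaves the cut-offs for abnormal ECG values to the SAP, and the combined document gives none for HR or PR.

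**The concern.** Section 1.3.2.4 treats transient slowing of heart rate and AV conduction as the leading safety signal of the drug. Safety is a main objective, and this is the first trial of the drug in chronic GVHD. Yet the one planned count of subjects crossing an HR or PR threshold after the first dose uses a single tracing taken after the stated nadir window. A subject who crosses at 2 h and has recovered above the threshold by 3 h is not counted. Every other time point in the core-period list is pre-dose, or is Week 24, when no dose is taken at the visit. With about 30 subjects, one uncounted subject moves the reported proportion by 1/30 = 3.3 percentage points, always in the favourable direction.

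**Working it through.** The plan states no HR or PR outlier rate, so there is no figure to reproduce. The check has four steps.

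**1. Timing.** Nadir at 1.5–2.5 h (Section 1.3.2.4); counting time 3 h (Section 6.2.3). Delay: 3 − 2.5 = 0.5 h to 3 − 1.5 = 1.5 h. Of the hourly ECGs at 1, 2, 3 and 4 h, only the 2 h tracing lies inside the window. The count uses 1 of at least 4 post-dose tracings per subject, or 30 of at least 30 × 4 = 120 for 30 subjects. That describes coverage and does not measure bias.

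**2. Direction.** Any subject abnormal at 3 h is also abnormal at one or more of the post-dose ECGs. Hence P(abnormal at 3 h) ≤ P(abnormal at any post-dose ECG). They are equal only if no subject crosses at another hour without also crossing at 3 h. This holds for HR and PR whatever the cut-off.

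**3. Effect remaining at 3 h.** Let n be the nadir time and r the recovery time (6–10 h, Section 1.3.2.4). The shape of recovery is an assumption. Linear: 1 − (3 − n)/(r − n). Exponential with 90% resolved at r: 0.1^((3 − n)/(r − n)).

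| n (h) | r (h) | Linear | Exponential |
|---|---|---|---|
| 1.5 | 6 | 0.67 | 0.46 |
| 1.5 | 10 | 0.82 | 0.67 |
| 2.0 | 6 | 0.75 | 0.56 |
| 2.0 | 10 | 0.88 | 0.75 |
| 2.5 | 6 | 0.86 | 0.72 |
| 2.5 | 10 | 0.93 | 0.86 |

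So 67–93% of the peak fall remains at 3 h under linear recovery, and 46–86% under exponential recovery.

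**4. Illustration for HR.** None of these inputs is in the documents except the nadir and recovery times and the exclusion of resting HR below 50 bpm. Assumed: baseline HR mean 75, SD 10; mean peak fall 8 (SD 5) or 12 (SD 6) bpm; linear onset and recovery; within-subject noise SD 0 or 3 bpm; cut-off below 50 or below 45 bpm. The ratio column spans all these settings. The count columns are for the cut-off of 50 bpm.

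| Nadir / recovery (h) | 3 h count ÷ any 1–4 h count | Expected of 30, 3 h | Expected of 30, any 1–4 h |
|---|---|---|---|
| 1.5 / 6 | 0.35–0.55 | 0.7–1.8 | 1.3–3.6 |
| 2 / 8 | 0.50–0.67 | 1.2–2.8 | 1.8–4.5 |
| 2.5 / 10 | 0.73–1.00 | 1.5–3.5 | 1.5–4.2 |

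With the nadir at 2.5 h and no noise nothing is lost, because the 2 h tracing is still on the way down (2/2.5 = 0.80 of the peak fall, against 0.93 at 3 h). With the nadir at 1.5 h the loss reaches about 65%.

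**The case against.** The strongest reply is that a clinically important event at 1 or 2 h has several routes into the report. The hourly summaries would normally show the lowest HR and longest PR at each hour, and all values are listed. New morphological findings, other ECG abnormalities and heart-rate adverse events of special interest are not tied to 3 h. Under Section 5.1.10.1 an ECG-documented HR below 40 bpm at any time leads to discontinuation, so any resulting adverse event is tabulated. Day 1 is also a 2 mg titration dose meant to reduce first-dose effects, so crossings may be few.

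Much of this stands. A reader might infer that QTc outliers are also seen only at 3 h; they are not, because separate QTc threshold and increase counts run from first intake. A reader might infer that the 1 h and 2 h data are reduced to means or lost; Sections 11 and 11.2.10.3.2 show otherwise. A reader might also infer that the extension is left out; Sections 11.2.5 and 11.2.10.3.3 cover it in general terms.

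What the reply does not supply is a count. A minimum shows one subject's extreme at one hour, not how many subjects crossed a threshold at any hour. The event categories carry no HR or PR threshold. Leaving cut-offs to the SAP does not reopen the hour, which Sections 6.2.3, 11.2.2 and 11.2.10.3.3 already fix.

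**Conclusion.** The point holds for HR and PR. The planned Day 1 outlier proportions can only equal or understate the proportions over all post-dose ECGs, and no other planned output is a defined HR or PR threshold count at the remaining post-dose hours.

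The direction needs no assumption. The size is unknown, because there is no cut-off and no expected rate; the illustration runs from no loss to about 65% and rests on assumed heart-rate distributions. It would be tempting to say that the rates will be materially understated, but the documents do not support that, since equality is possible. For PR the argument is weaker still: the inequality holds, but the 1.5–2.5 h nadir is stated for sinus rate, and the timing of the PR effect is only implied by its accompanying the fall in rate. This is a gap in how first-dose effects are tabulated, not a failure to record or detect them.

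**What to change.** In the SAP, count HR and PR notable abnormalities over all post-dose ECGs on Day 1, at EX-1 and on each monitored re-initiation day. Report the worst value per subject (lowest HR, longest PR) and the count by hour, with 3 h kept as one of the hourly columns. State the HR and PR cut-offs there too. Align the synopsis and Sections 6.2.3, 11.2.2 and 11.2.10.3.3 at the next amendment.

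The cost is small. The tracings are already recorded and centrally read, so the work is a few more table rows. The SAP is approved before database lock (Section 11), so the change can be made there first. Changing the protocol text needs a written amendment under Section 13.6, which is why it can wait for the next one. The reported outlier rates may become slightly less favourable.
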